**9.13 ANALYSES FOR THE OUTCOMES OF THE PART 1 STUDY**

The primary outcome measure of the Part 1 study is Maximum Tolerable Dose (MTD) by maximum percentage of BSA treated, by evaluation of dose-limiting toxicity (DLT) of AMTX-100 CF (1.1% w/w concentration) based on the safety profile.

AEs will be classified by system organ class (SOC) and preferred term (PT) according to the most recent version of MedDRA dictionary. All AEs that met the dose escalation stopping criteria will be summarized using MedDRA SOC & PT and by relationship to the study treatment for the safety population.

[REDACTED]

- [REDACTED]
- [REDACTED]
- [REDACTED]

[REDACTED]

[REDACTED]

[REDACTED]

[REDACTED]

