#### 10.1.4 CAUSALITY ASSESSMENT

Adverse events will be assigned a relationship (causality) to the study treatment. The Principal Investigator must review each AE and make the determination of relationship of the event to the study treatment. Relationship of AEs to study treatment will be classified as follows:

- 1. Definitely related:** This category applies to those AEs that the Investigator feels are incontrovertibly related to the study treatment. An AE may be assigned an attribution of definitely related if or when it meets all of the following criteria: (1) it follows a reasonable temporal sequence from administration of the study treatment; (2) it could not be reasonably explained by the known characteristics of the subject's clinical state, environmental or toxic factors, or other modes of therapy administered to the subject; (3) Disappears or is decreased upon discontinuation of the study treatment; (4) it follows a known response pattern to treatment with the study treatment.
- 2. Probably related:** This category applies to those AEs which, after careful medical consideration at the time they are evaluated, are felt with a high degree of certainty to be related to the study treatment. An AE may be considered probable if or when (must have three): (1) it follows a reasonable temporal sequence from administration of the study treatment. (2) It could not readily have been produced by subject's clinical state, environmental or toxic factors, or other therapies administered to the subject. (3) Disappears or is decreased upon discontinuation of the study treatment. (4) It follows a known response pattern to treatment with the study treatment.
- 3. Possibly related:** This category applies to those AEs which, after careful medical consideration at the time they are evaluated, are judged unlikely but cannot be ruled out with certainty to the study treatment. An AE may be considered possible if or when (must have two): (1) it follows a reasonable temporal sequence from administration of the study treatment. (2) It could not readily have been produced by subject's clinical state, environmental or toxic factors, or other therapies administered to the subject. (3) Disappears or is decreased upon discontinuation of the study treatment. (4) It follows a known response pattern to treatment with the study treatment.

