4. **Unlikely related:** In general this category can be considered applicable to those AEs which, after careful medical consideration at the time they are evaluated, are judged likely to be unrelated to the study treatment. An AE may be considered unlikely if or when (must have two): (1) it does not follow a reasonable temporal sequence from administration of the study treatment. (2) It could not readily have been produced by subject's clinical state, environmental or toxic factors, or other therapies administered to the subject. (3) Disappears or is decreased upon discontinuation of the study treatment. (4) It does not follow a known response pattern to treatment with the study treatment.
5. **Unrelated:** This category applies to those AEs which, after careful consideration at the time they are evaluated, are clearly and incontrovertibly due to extraneous causes (disease, environment, etc.) and determined with certainty to have no relationship to the study treatment.

[figure not shown]

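### Two of the four criteria for an adverse event 'Unlikely related' to treatment were left unreversed, so they count evidence for a drug cause as evidence against one

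*Protocol*

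**What the plan says.** Protocol section 10.1.4 sorts adverse events into five categories by their relationship to study treatment. Four of them come with a numbered list of criteria: *Definitely* requires all four, *Probably* three, *Possibly* two and *Unlikely* two.

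- **Criterion (2) under *Probably* and *Possibly*:** "It could not readily have been produced by subject's clinical state, environmental or toxic factors, or other therapies administered to the subject". *Definitely* words the same idea slightly differently.
- **Criteria (3) and (4) under *Definitely*:** "3) Disappears or is decreased upon discontinuation of the study treatment; (4) it follows a known response pattern to treatment with the study treatment". *Probably* and *Possibly* use the same two.
- ***Unlikely*, general description:** events that "are judged likely to be unrelated to the study treatment".
- ***Unlikely*, start of the list:** "it does not follow a reasonable temporal sequence from administration of the study treatment. (2) It could not readily have been produced by". Criterion (1) is negated; (2) is not.
- ***Unlikely*, end of the list:** "3) Disappears or is decreased upon discontinuation of the study treatment. (4) It does not follow a known response pattern to treatment". Criterion (3) is not negated; (4) is.
- ***Possibly*, general description:** events that "are judged unlikely but cannot be ruled out with certainty to the study treatment".

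On who decides: "The Principal Investigator must review each AE and make the determination of relationship of the event to the study treatment". On use: protocol section 9.13 summarises the Part 1 events that met the dose-escalation stopping criteria "by relationship to the study treatment for the safety population". Nothing visible elsewhere in the protocol, or in the SAP, redefines or corrects the *Unlikely* category.

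**The concern.** One fact cannot be evidence for a drug cause in one category and evidence against it in the next. Having no other ready explanation and improving when treatment stops are two of the four arguments for relatedness under *Probably* and *Possibly*. Under *Unlikely* the same two statements, in the same words, satisfy the requirement of two criteria on their own. That contradicts the category's own description. The rule is present and wrong; it is not a missing detail.

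The boundary on the other side is also blurred, because *Possibly related* is itself described as a judgement of unlikely.

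What is at stake is consistency. Investigators who follow the list and investigators who follow the general description can class like events differently. The visible place where this would show is the Part 1 by-relationship table. Part 1 has 5 subjects per cohort (protocol section 9.3), so one event classed differently can change that table.

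**Working it through.** The plan gives no figure to reproduce. The check compares the wording and then counts which combinations of facts satisfy which list.

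**Inputs (protocol section 10.1.4).** Code each fact 1 for yes and 0 for no:

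- T: reasonable timing
- N: no other ready explanation
- D: disappears or lessens on stopping
- K: fits a known response pattern

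The required numbers of criteria are read as minimums.

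**Formulas.**

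- Related score: R = T + N + D + K. *Definitely* if R = 4, *Probably* if R ≥ 3, *Possibly* if R ≥ 2.
- *Unlikely* as written: U = (1−T) + N + D + (1−K), met if U ≥ 2.
- *Unlikely* with (2) and (3) both reversed: U* = (1−T) + (1−N) + (1−D) + (1−K) = 4 − R, met if U* ≥ 2.

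| T N D K | R | U (written) | Meets *Unlikely*, written | U* (both reversed) | Meets *Unlikely*, reversed |
|---|---|---|---|---|---|
| 1 1 1 1 | 4 | 2 | yes | 0 | no |
| 1 1 1 0 | 3 | 3 | yes | 1 | no |
| 1 1 0 1 | 3 | 1 | no | 1 | no |
| 1 0 1 1 | 3 | 1 | no | 1 | no |
| 0 1 1 1 | 3 | 3 | yes | 1 | no |
| 1 1 0 0 | 2 | 2 | yes | 2 | yes |
| 1 0 1 0 | 2 | 2 | yes | 2 | yes |
| 1 0 0 1 | 2 | 0 | no | 2 | yes |
| 0 1 1 0 | 2 | 4 | yes | 2 | yes |
| 0 1 0 1 | 2 | 2 | yes | 2 | yes |
| 0 0 1 1 | 2 | 2 | yes | 2 | yes |
| 1 0 0 0 | 1 | 1 | no | 3 | yes |
| 0 1 0 0 | 1 | 3 | yes | 3 | yes |
| 0 0 1 0 | 1 | 3 | yes | 3 | yes |
| 0 0 0 1 | 1 | 1 | no | 3 | yes |
| 0 0 0 0 | 0 | 2 | yes | 4 | yes |

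**As written.**

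- Eleven patterns have R ≥ 2; of these, 5 + 2 + 1 = 8 also meet *Unlikely* (R = 2, 3 and 4 respectively).
- Five patterns have R ≥ 3; 3 also meet *Unlikely*, including the single R = 4 pattern.
- All 4 patterns with N = D = 1 meet *Unlikely*.
- Timing alone and known pattern alone meet neither *Possibly* nor *Unlikely*, so 2 weakly related patterns have no list.
- The ordering is upset too: an event with T, N and D present scores U = 3, more than an event with nothing in favour of relatedness (U = 2).

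**Dropping implausible patterns.** A known response pattern without reasonable timing (K = 1, T = 0) is odd. Without those 4 patterns, the overlap is (8−3) of (11−3) = 5 of 8 for *Possibly* and (3−1) of (5−1) = 2 of 4 for *Probably*.

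**Reversing one criterion only.** With only (2) reversed, patterns 1110, 1011 and 0111 each score 2 and still qualify as *Unlikely*: 3 of 5. With only (3) reversed, 1110, 1101 and 0111 do: again 3 of 5.

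**Reversing both.** The overlap with *Probably* is 0 of 5 and with *Definitely* 0 of 1, and no pattern is left without a list. All 6 patterns with R = 2 now meet both *Possibly* and *Unlikely*; as written, 5 of them do.

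**The case against.** The strongest reply is that the list does not decide anything by itself. The category is for events that, after medical consideration, are thought unrelated; the text is permissive, and the Principal Investigator decides. Two criteria can be read as a minimum on top of that judgement. On that reading an event with all four supporting facts would never be classed as *Unlikely*. This stands as far as it goes: the counts above are overlaps between lists, not predicted misclassifications, and they give rare and common patterns equal weight. It does not rescue the text. These criteria are the only visible guidance for the judgement, and half of them point the wrong way.

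The second reply is that the consequence is small, and that also stands in part. Adverse event and serious adverse event collection does not depend on relatedness, and the SAP plans no inferential safety statistics for Part 1. The one visible use is the section 9.13 table. The lists of further adverse event summaries, the dose-limiting toxicity rule and most of the monitoring committee text are blacked out, so a wider effect can be neither shown nor excluded. The SAP was also prepared from protocol version 2.0, whose causality wording is not available, so it is unknown which wording applied to the Part 1 events.

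Third, the correction does not sharpen the line between *Possibly* and *Unlikely*: ties there go from 5 to 6. That is correct, and follows from both lists asking for two of four. The gain lies at *Probably*, at *Definitely* and in the 2-pattern gap.

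**Conclusion.** The point holds. As written, criteria (2) and (3) of *Unlikely related* contradict the category they define. The *Unlikely* list admits 8 of the 11 *Possibly* patterns and 3 of the 5 *Probably* patterns, including the *Definitely* pattern, and leaves 2 weakly related patterns in neither *Possibly* nor *Unlikely*.

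The counts assume that the required numbers are minimums, that each fact can be answered yes or no (which sets aside events during which treatment was never stopped), and that criterion (2) of *Definitely* records the same fact as criterion (2) elsewhere. The contradiction itself needs only the comparison of wording.

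It should be corrected, because the definition applies to every adverse event. The demonstrable effect is limited to possible inconsistency in one Part 1 table; no effect on dose escalation or on overall adverse event reporting can be shown from the visible text.

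**What to change.** In protocol section 10.1.4, category 4, reverse both criteria:

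- **(2)** the event could readily be explained by the patient's condition, by environmental or toxic factors, or by other therapy;
- **(3)** the event does not resolve or lessen once study treatment is discontinued.

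Both changes are needed. Then reword the general description of *Possibly related* so that it no longer calls the relationship unlikely, and say that an event with two facts on each side is left to the investigator's judgement between *Possibly* and *Unlikely*.

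The cost is two criteria and one phrase in a single section, made through a written, dated amendment under section 13.3, with ethics approval unless one of that section's exceptions applies. Any event already classed as *Unlikely* under the present wording should be looked at again.

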#### 10.1.5 TREATMENT GIVEN AS A RESULT OF THE EVENT

The event impact in terms of treatment provided will be as either: none, medication administered, non-medication therapy administered, surgery, or other (with a specification).

#### 10.1.6 OUTCOME ASSESSMENT

[figure not shown]
The outcome of the event will be assessed as either: resolved, resolved with sequelae, ongoing, or death. Only one AE per subject is allowed to have an outcome assessment as "death." If there are multiple causes of death for a given subject, only the primary cause of death will have an outcome of death.

#### 10.1.7 EXPECTED /ANTICIPATED ADVERSE EVENTS

#### 10.1.8 APPLICATION SITE REACTIONS

For this population, presence of signs/symptoms similar to application site reactions at the eczema lesions at the baseline is expected. Only significant worsening of these signs/symptoms from the baseline per the investigator would be considered adverse events.

[REDACTED]

[REDACTED]

## 10.2 SERIOUS ADVERSE EVENTS

A SAE is defined as any AE that:

- Results in death
- Is life threatening (the subject is at immediate risk of dying from the AE)
- Requires subject hospitalization or prolongs existing hospitalization
- Results in persistent or significant disability/incapacity
- Is a congenital anomaly/birth defect
- Important medical events that may not result in death, be life-threatening, or require hospitalization may be considered serious when, based upon appropriate medical judgment, they may jeopardize the subject and may require medical or surgical intervention to prevent one of the outcomes listed in this definition

## 10.3 REPORTING OF SERIOUS ADVERSE EVENTS (SAE)

The Investigator is required to report all SAEs that occur during the time period specified in [Section 10.1.1](#). Once the Investigator becomes aware of an SAE, he/she must report the SAE to Amarex Safety Department within 24 hours:

CRO Medical Monitor	[REDACTED] Amarex LLC 20201 Century Boulevard, 4 th [name] 20874 [REDACTED]
----------------------------	--

The Amarex Medical Monitor may request additional supporting documentation as it becomes available, such as lab reports, discharge summary, hospital notes, etc.

The Investigator is also responsible for reporting all SAEs to the appropriate Institutional Review Board (IRB) in accordance with local laws and regulations. The Investigator is responsible for maintaining documentation in the study file that indicates the IRB has been properly notified.

## **10.4 SAE FOLLOW-UP**

All subjects experiencing an SAE, including the discontinued subjects, must be closely followed until sufficient information is obtained to indicate a return to normal status or until the event stabilizes at a level acceptable to the investigator (i.e., recovery, return to baseline status, no further improvement expected, or death).

For each SAE indicated as an unresolved event on the initial report, regardless of whether the subject completed the study or withdrew, the site should submit a follow-up report with updated information.

## **11 DIRECT ACCESS TO SOURCE DATA/DOCUMENTATION**

Subjects will be identified on CRFs by a unique subject identification number and on source documents by name and date of birth. No personal identifier will be used in any publication or communication used to support this research study. The subject identification number will be used if it becomes necessary to identify data specific to a single subject.

The monitors, auditors, personnel authorized by the Sponsor, the local IRB, and the FDA are eligible to review medical and research records related to this study as a part of their responsibility to protect human subjects in clinical research and will be given direct access to source data and documentation (e.g., medical charts/records, printouts etc.) for source data verification, provided that subject confidentiality is maintained in accordance with local requirements. Access to electronic medical records may be governed by institution policy and each site will be required to ensure access while remaining compliant with institutional requirements.

## 12 DATA SAFETY MONITORING COMMITTEE (DSMC)

In Phase I (Part 1) of the study, the study will be monitored by an independent Data Safety Monitoring Committee (DSMC) to ensure patient safety. The CRO is responsible for the overall management of the DSMC, including development of its charter and membership selection. The DSMC will be managed in conformance with the FDA guidelines for DSMC independence, management, and oversight.

[REDACTED]

[REDACTED]

[REDACTED]

[REDACTED]

- [REDACTED]
- [REDACTED]
- [REDACTED]
- [REDACTED]

[REDACTED]

In Phase II (Part 2) of the study, the DSMC will consider safety data generated during Part 2 of the study and to make recommendations about the IA.

[REDACTED]

## 13 QUALITY CONTROL AND QUALITY ASSURANCE

### 13.1 MONITORING REQUIREMENTS

In an effort to fulfill the obligations outlined in 21 CFR Part 312 and ICH guidelines which require the Sponsor to maintain current personal knowledge of the progress of a study, the Sponsor's designated monitor will visit the center(s) during the study as well as maintain frequent telephone and written communication. The Investigator will permit the Sponsor to monitor the study as frequently as is deemed necessary and provide access to medical records to ensure that data are being recorded adequately, that data are verifiable and that protocol adherence is satisfactory.

The Investigator will permit representatives of the Sponsor and/or designated CRO to inspect all CRFs and corresponding study subject original medical records (source documents) at regular intervals throughout the study. Subject original medical records and other relevant data must be available to support all data recorded in the CRF. In addition to the original medical records, these data may include but are not limited to, study, laboratory and diagnostic reports, wound images and tracings, etc.

Site inspections serve to verify strict adherence to the protocol and the accuracy of the data being entered on the CRFs, in accordance with federal regulations. A Monitoring Log will be maintained at each study site that the monitor will sign, date, and state the type of visit.

The Investigator should be aware that the study site and subject records may be inspected by the Sponsor and or representatives of the designated CRO, FDA, or other regional regulatory authority.

The final statistical analysis of data will be performed after all clinical monitoring has been completed, all data queries have been resolved, and all data have been verified (Quality Control checked) prior to formal database lock. The Sponsor will authorize the final database lock.

### 13.2 ACCEPTABILITY OF CASE REPORT FORMS

All CRFs will be completed as soon as possible after the subject's visit. Corrections to data on the CRFs will be made according to standard data correction procedures. The Investigator will review CRFs to indicate that, to his/her knowledge, they are complete and accurate. CRFs will be reviewed by the Sponsor's or designated CRO's monitor, who will make a decision as to their acceptability.

### 13.3 MODIFICATION OF PROTOCOL

The Investigator will not modify or alter this protocol without first obtaining the concurrence of the Sponsor. Approval by the Investigator's IRB must also be obtained prior to implementation of the change, with two exceptions:

1. When necessary to eliminate apparent immediate hazard to the subject; or
2. When the modification does not involve the subject's participation in the trial.

An amendment may also require modification of the ICF. The Investigator will provide an approval letter for the amendment and revised ICF, if applicable, to the Sponsor. An amendment must be in writing and it must be dated by both the Sponsor and the Investigator. If necessary, the Sponsor will submit protocol amendments to FDA and other appropriate regulatory authorities and notify other Investigators using this protocol.

#### **13.4 REPORTING PROTOCOL DEVIATIONS**

The Investigator is obligated to follow the protocol without departure from the requirements written in the protocol. If the Investigator deviates from the protocol requirements, the Sponsor will make the determination as to whether the subject will continue in the study. The Sponsor also has the right to discontinue the subject for protocol violations. The IRB may also have to be contacted if safety to the subject or if the scientific soundness of the study is involved. All protocol deviations must be documented in the CRFs.

## **14 ETHICS AND REGULATORY REQUIREMENTS**

This study is to be conducted in accordance with the specifications of this protocol and in accordance with principles consistent with the Declaration of Helsinki, GCP, 21 CFR 312, ICH E6, HIPAA regulations in 45 CFR Part 164, and the Belmont Principles of respect for persons, beneficence, and justice. No protocol changes will be implemented without the prior review and approval of the IRB, except where it may be necessary to eliminate an immediate hazard to a research subject. In such a case, the change will be reported to the IRB as soon as possible, according to IRB regulations. Additionally, all study products used in this study are manufactured, handled and stored in accordance with applicable Good Manufacturing Practices (GMP) and the products provided for this study will be used only in accordance with this protocol.

### **14.1 INSTITUTIONAL REVIEW BOARD/INDEPENDENT ETHICS COMMITTEE**

The Principal Investigator will provide the Institutional Review Board/Independent Ethics Committee (IRB/IEC) with all appropriate materials as required by their IRB/IEC, including but not limited to the clinical study protocol, ICFs, and any advertising materials. The study will not be initiated until the IRB/IEC provides written approval of the aforementioned documents and until approval documents have been obtained by the Principal Investigator and Sponsor or Sponsor designee. The Investigator will not participate in the decision. If the Investigator is an IRB or IEC member, documentation must be provided indicating recusal from the approval process. Appropriate reports on the progress of this study by the Principal Investigator will be made to the IRB/IEC as required by local and applicable government regulations and in agreement with policy established by the Sponsor. The Investigator is required to maintain an accurate and complete record of all written correspondence to and received from the IRB/IEC and must agree to share all such documents and reports with the Sponsor.

No changes from the final approved protocol will be initiated without the IRB/IEC's prior written approval or favorable opinion of a written amendment, except when necessary to eliminate immediate hazards to the subjects or when the change involves only logistics or administration.

